The validity of a triage system refers to its ability to reflect the true urgency of the patient's condition. A major challenge in validity assessment is the absence of a definitive or 'gold standard' measure of urgency.² A range of surrogate markers have therefore been used to assess criterion and predictive validity, namely ED outcomes such as admission rate, mortality and length of stay. Some authors have suggested that a Delphi approach might also be useful for the evaluation of triage systems in developing settings.⁸

Several studies have calculated under- and over-triage rates as a measure of validity.⁹⁻¹² These typically use acceptable limits defined by the American College of Surgeons Committee on Trauma (ACS COT) as a reference standard.¹³

Emergency care and triage in Papua New Guinea

Papua New Guinea (PNG), a Pacific Island Country (PIC) with a population of approximately 8 million, is faced by significant challenges in healthcare delivery. These include under-resourcing, a limited health workforce, a high burden of communicable disease (including significant rates of HIV/AIDS and tuberculosis) as well as an increasing prevalence of non-communicable illness and injury.¹⁴

Despite an increasing number of emergency physicians, most provinces outside of Port Moresby (the nation's capital) have under-developed primary and secondary care systems to facilitate emergency care.¹⁵ There is little data on the epidemiology of emergency presentations, and most EDs are not utilising triage scales. Triage has been identified as a priority for emergency care development for PICs, including PNG [personal communication, [name]].

Aims

The primary objective of this study is to measure the impact of a triage system on process indicators and clinical outcomes in a regional ED in PNG.

The secondary objective of this study is to determine the validity and reliability of the World Health Organization Triage Scale in this setting.

Methods

Setting

This study will be conducted in the ED of the Mount Hagen Provincial Hospital (MHPH) in the Western Highlands Province of PNG. The hospital is managed by the Western Highlands Provincial Health Authority (WHPHA).

Mount Hagen is the third largest city in PNG, with a population of approximately 50,000. It is the capital of the Western Highlands Province (population approximately 400,000), and a major administrative centre for the Highlands region.

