MHPH is the city's major health facility. There is limited primary care infrastructure within the province, so patients rely on MHPH for the majority of their healthcare needs. As in other parts of the country, there is a large burden of both communicable and non-communicable disease, including HIV/AIDS, tuberculosis diabetes, cardiovascular disease, chronic respiratory conditions and trauma.

The ED receives approximately 150 presentations per day, and is staffed by one emergency physician, three registrars (specialists in training), five health extension officers (HEOs) and approximately thirty nurses. The ED has recently been redeveloped, and now includes four resuscitation bays, 16 acute beds and five short-stay beds. Basic pathology and radiology services are available.

Under current arrangements, the ED has no triage system and manual data collection processes are leading to gross under-reporting of presentation numbers. Major challenges for the ED include understaffing, a large burden of primary care patients and access block.

A new electronic database of ED patients has recently been implemented to capture basic attendance data. This system will facilitate data capture for the study.

Design

This study will utilise pre-post intervention methodology and will be prospectively registered as a clinical trial with the United States National Library of Medicine Clinical Trials Register at clinicaltrials.gov.

Pre-intervention

A new MHPH ED Patient Registration and Triage Form (PRTF) will be created to facilitate the new system and capture relevant data items, such as demographics and initial vital signs (Appendix 1). This form will be based on an existing MHPH ED discharge form, as well as a triage form successfully implemented in another Pacific setting.⁷

Data from the PRTF will be entered by ward clerks into the ED's electronic patient registration system (recently implemented as part of a hospital-wide data improvement project). This system forms part of the MHPH medical records database.

After a trial period of staff testing the new form, the PRTF will be implemented and baseline data captured in the database. During this period, the PRTF will not include any triage information (Appendix 1A). Based on a power calculation (see below), two months of pre-intervention data will be collected.

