In order to identify patients who meet inclusion criteria, as defined below, the PRTF will require the treating clinician to indicate whether the patient had one of the ten sentinel conditions (listed below).

Intervention

The intervention will comprise implementation of a new triage and patient flow system facilitated through staff training and clinical redesign.

The three-tier World Health Organization Triage Scale (WHOTS) will be used as the triage instrument. This tool, developed collaboratively by the WHO, International Committee of the Red Cross (ICRC) and Médecins Sans Frontières (MSF), incorporates features of the SATS but has been modified for application in a wide variety of RL settings. WHOTS documents are provided in Appendix 2.

At the end of the baseline data collection period, MHPH ED staff will be trained in the new system. A variety of ED clinicians (who will subsequently take on the triage role) will be the focus of this training program. This will include nurses, community health workers and health extension officers in order to provide flexibility in the staffing model. Triage training will be delivered by an experienced Australasian volunteer nurse(s) and comprise workshops on triage principles, paper-based scenarios and simulation exercises.

Signage will be introduced to facilitate the new system of flow, and the ED will begin utilising the version of the PRTF that incorporates triage data (Appendix 1B). The triage instrument will be piloted over a one-month period (approximately). Modifications will be made based on real-time feedback as well as observations by the visiting team.

Post-intervention

After completion of the trial period, the new triage and flow system will be implemented under the leadership of local clinicians. The ED registration database will be updated to capture triage category data.

For admitted patients, hospital length-of-stay (LOS) and inpatient mortality data will be obtained from the WHPHA medical records database. These patients will be identified by the patient's unique hospital identification number.

Outcomes

Primary objective

The primary outcome will be time-to-assessment (TTA) by an ED clinician for ten time-critical conditions:

- Severe trauma
- Major burns
- Severe head injury
- Ruptured ectopic pregnancy
- Septic shock
- Myocardial infarction
- Severe asthma/COPD
- Severe pneumonia
- Meningitis
- Appendicitis

Pragmatic definitions for these conditions are provided at Appendix 3.

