The primary outcome will also be analysed by the proportion of patients with these clinical syndromes that are seen within a clinically appropriate timeframe (defined as 15 minutes, as discussed below).

Secondary outcomes will include:

- Length of hospital stay
- ED mortality
- Inpatient mortality

These are also defined in Appendix 3.

Secondary objectives

Validity of the WHOTS will be assessed through its ability to predict ED outcomes. This will include the relationship between triage category and admission rates and ED mortality.

Under- or over-triage rates will also be calculated using disposition as a reference standard. This approach has limitations (see below) but is widely used in triage research.

Over-triage will be defined as the proportion of emergency (category 1) patients who are discharged. Under-triage will be defined as the proportion of non-urgent (category 3) patients who are admitted. Rates will be compared with the acceptable under- and over-triage rates recommended by ACS COT¹³ (and widely referenced in triage research) and then benchmarked against other published data. This approach has limitations (given that not all category 1 patients will require admission, and many category 3 patients could reasonably be expected to; recommendations for triage in trauma do not necessarily apply to other disease categories; and the performance targets provided by an American society do not necessarily apply to other contexts) but will be undertaken to enable comparison with other triage research from LMICs.

Reliability will be assessed through inter-rater agreement between two local triage nurses as well as a local nurse and independent expert triage nurse.

Analysis

All data will be obtained from the MHPH medical records database. Hospital medical records staff will export de-identified data into an Excel document, which will be provided to researchers and stored on a secure, password protected Monash University drive. All data will be analysed using Stata. No identifiable data will be available to the researchers.

Primary objectives

For the primary outcomes, Student's t-test will be used to compare the difference in TTA for the ten sentinel conditions (assuming parametric data). Chi-Square will be used to determine the difference in proportions of patients seen within 15 minutes.

For the secondary outcomes of ED mortality, hospital mortality and hospital LOS, Student's t-test or Chi-Square will be used as appropriate.

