Secondary objectives

For predictive validity, Chi-Square and correlation coefficient derived by Cramer's V will be used to investigate the relationship between triage category and admission rates & ED mortality.

Under- and over-triage rates will be calculated using the definitions above. Acceptable limits set by the American College of Surgeons Committee on Trauma (an under-triage rate of less than 10% and an over-triage rate of 30–50%) will be used as the reference standard.¹³ This approach is consistent with that used in other triage research, despite the limitations discussed above.^{9–12}

For reliability, the modified Kappa statistic will be used to test inter-rater agreement between triage nurses.

Sample size

It is estimated that approximately 15 patients per day present with one of the ten sentinel syndromes and wait an average of 20 minutes to be seen. A clinically significant improvement in the TTA for these patients is thought to be five minutes. Although Australasian guidelines recommend that high acuity presentations (equivalent to categories one and two in the Australasian Triage Scale) are seen within 10 minutes of arrival,¹⁶ a target of 15 minutes is thought to be acceptable in the resource limited context of MHPH.

Based on these figures, a sample size of 34 (17 per group) will be required to demonstrate a clinically significant decrease in TTA for the selected time-critical conditions at an alpha of 0.05 and beta of 0.8.

The primary outcome will also be analysed by the proportion of patients seen within 15 minutes of arrival. Assuming baseline performance is 45%, an absolute improvement of 10% (to 55%) will require a sample size of 784 (392 per group) at an alpha of 0.05 and beta of 0.8.

The secondary outcome of mortality will require a larger sample. In order to demonstrate an absolute reduction in mortality of 5% (from an estimated baseline mortality rate of 15%), a sample size of 1372 (686 per group) is required at an alpha of 0.05 and beta of 0.8.

To ensure a satisfactory sample size to demonstrate all outcomes, pre- and post-intervention periods of 8 weeks will be utilised. This is based on a total sample size of 1372 for the secondary outcome of mortality (with a buffer of 10%) at an estimated presentation rate of 15 per day. This requires pre- and post-intervention periods of at least 50 days.

Ethics

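### Three cadres will triage but only nurses are rated for reliability, so the Kappa does not cover all users of the scale

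*Combined protocol and SAP*

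**What the plan says.** **Who will triage.** Under Design, Intervention: "A variety of ED clinicians (who will subsequently take on the triage role) will be the focus of this training program". The next sentence names the cadres and gives the reason: "This will include nurses, community health workers and health extension officers in order to provide flexibility in the staffing model". Spreading triage over several cadres is thus a deliberate part of the intervention.

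**Who will be rated.** Under Outcomes, Secondary objectives: "Reliability will be assessed through inter-rater agreement between two local triage nurses as well as a local nurse and independent expert triage nurse". Under Analysis, Secondary objectives: "For reliability, the modified Kappa statistic will be used to test inter-rater agreement between triage nurses". The two sections agree with each other.

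**What is to be concluded.** The secondary objective in the Aims is to "determine the validity and reliability of the World Health Organization Triage Scale in this setting".

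**Staffing.** The Setting section lists "five health extension officers (HEOs) and approximately thirty nurses". It gives no number of CHWs, and the plan does not say what share of triage each cadre will do.

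**The concern.** The background section on evaluating triage systems treats reliability as the chance that a second assessment of the same patient gives the same category. In this ED, on the plan's own staffing model, the second assessor could be a nurse, an HEO or a CHW. A Kappa from nurse pairs leaves out every pair that contains an HEO or a CHW. It also leaves out any comparison of those two cadres with the expert.

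Two things are at stake. First, the reliability result would be narrower than the objective it is meant to answer. Second, the two halves of that objective would describe different raters. The validity, over-triage and under-triage analyses use whatever category was assigned, by any cadre, while the Kappa speaks for nurses alone. The Conclusion says that there are no published performance data on this scale and that the results should inform other settings, so a reader needs to know which users the figure covers.

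**Working it through.** The plan states no number of paired ratings, target value or precision for the Kappa. The Sample size section deals only with time to assessment, the 15-minute proportion and mortality. There is therefore no figure to reproduce, and the check is first a comparison of text.

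**Step 1: set the sections side by side.**

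| Question | Section | Answer |
|---|---|---|
| Who takes the triage role? | Design, Intervention | Nurses, HEOs, CHWs |
| Who is paired for agreement? | Outcomes, Secondary objectives | Local nurse with local nurse; local nurse with expert nurse |
| Whose agreement does Kappa test? | Analysis, Secondary objectives | Nurses |
| Are validity and mis-triage limited by cadre? | Outcomes and Analysis, Secondary objectives | No |
| Is the restriction acknowledged? | Limitations | No |

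No section plans a pair with an HEO or CHW, a cross-cadre pair or a Kappa by cadre.

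**Step 2: share of rater pairs covered.** With N nurses among T triagers, all triaging equally, the share of nurse-nurse pairs among possible pairs of different triagers is w = N(N − 1) / [T(T − 1)]. N = 30 and 5 HEOs come from Setting. The number of CHWs is an assumption, so a range is shown.

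| CHWs (assumed) | T | w | Pairs left out |
|---|---|---|---|
| 0 | 35 | 30×29 / (35×34) = 870/1190 = 73.1% | 26.9% |
| 5 | 40 | 870 / (40×39) = 870/1560 = 55.8% | 44.2% |
| 10 | 45 | 870 / (45×44) = 870/1980 = 43.9% | 56.1% |

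**Step 3: what this could do to the reported value.** As an approximation, treat the Kappa over all triagers as the pair-weighted average w·κ(nurse-nurse) + (1 − w)·κ(other pairs). The nurse-only value then differs from it by (1 − w) × [κ(nurse-nurse) − κ(other pairs)]. The Kappas below are assumed for illustration:

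- κ = 0.75 for nurse pairs and 0.45 for all others: the difference is 0.269 × 0.30 = 0.08, 0.442 × 0.30 = 0.13 and 0.561 × 0.30 = 0.17 for 0, 5 and 10 CHWs. The mixed values are about 0.67, 0.62 and 0.58.
- Equal κ in all pairs: the difference is zero.
- Other pairs agree better than nurse pairs: the sign reverses, and the nurse-only value is too low.

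The documents do not say which case applies.

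**The case against.** The strongest reply is that nurses will probably do most of the triage. Setting lists about thirty nurses against five HEOs, which is 5/35 = 14% non-nurses among those two groups, and does not list CHWs in the ED staffing at all. Training the other cadres for flexibility may mean little more than cover. On that view a nurse Kappa describes most of the scale's use. This stands in part: the Kappa does describe triage by nurses, and a reader who concludes that it says nothing about the scale as used in this ED goes further than the text allows. What remains is that it does not cover every cadre given the role.

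A reader might also infer two stronger things that the documents do not support:

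- *That the assessment rests on two individual nurses out of about thirty.* The wording most naturally describes a paired design, with two raters per patient, and the Analysis section gives no number of nurses. The gap in cadres exists on either reading.
- *That a nurse-only figure overstates reliability.* This needs pairs with other cadres to agree less well. The ED currently has no triage system and the plan cites no published performance data for this scale, so agreement is unknown for every cadre, nurses included.

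Finally, *triage nurse* may have been meant loosely, for anyone in the triage role. If so, the sponsor need only say so.

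**Conclusion.** The point holds in a limited form. The plan gives the triage role to three cadres, measures agreement within one, and states the objective without that restriction; no other section repairs or acknowledges this. The Kappa will not cover all users of the scale.

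The size and direction of the effect on the reported value are unknown. Coverage of about 73% of possible rater pairs, or about 56% or 44% with 5 or 10 CHWs, assumes that all named staff triage equally often. If nurses do a larger share than their headcount suggests, coverage is higher. The Kappa differences in the working are illustrations, not predictions.

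This concerns one secondary objective. The time-to-assessment and mortality analyses, and their sample sizes, are unaffected. It is a worthwhile, inexpensive improvement and not a flaw that threatens the trial.

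**What to change.** 1. In Outcomes, Secondary objectives, draw the local raters from all trained staff who perform triage, and include same-cadre, cross-cadre and local-versus-expert pairs.
2. In Analysis, Secondary objectives, replace *triage nurses* with *triage staff*. Make the overall Kappa the main reliability result, and report values by cadre as descriptive, with confidence intervals.
3. If this is impractical, add one sentence limiting the reliability conclusion to triage by nurses, and list the restriction under Limitations.

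**Cost.** The first two steps use staff already trained for the role, so the work is rostering and a few words of text. The rostering is still a burden in an ED that names understaffing among its main challenges. By-cadre estimates would be clearly less precise at a fixed number of paired ratings. If interval width varies as 1/√n, an even split over three cadres widens each interval by √3 ≈ 1.7. Three cadres give six local pair types plus three local-versus-expert types, and a split over all nine widens each by √9 = 3. That is why the overall Kappa should lead. The third step costs nothing.

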Ethics approval, including a waiver of consent, will be sought from Monash University. Consistent with local processes, approval to conduct this research will then be sought from the Medical Research Advisory Committee within the Papua New Guinean National Department of Health.

Limitations

This study has been designed to ensure it is methodologically robust. There are, however, several limitations that will need to be considered when interpreting the results.

The pre-post nature of the design means that the study may be subject to confounding. A particular risk is that a new and efficient triage system may prompt an increase in ED presentations, and a change in the overall acuity of the patient cohort. For this reason, the primary outcome will focus on ten clearly-defined time critical conditions.

Other factors may also influence the primary outcome, such as changes in staffing levels and acute fluctuations in demand for emergency care (for instance, in the setting of disaster or outbreak). Within the influence of the researchers, attempts will be made to control these factors and minimise variation across the study period.

There is a risk that the study will be subject to the Hawthorne effect. Although treating clinicians will be blinded to the primary outcome, they will have knowledge of the ten sentinel conditions by virtue of their inclusion on the PTRF. It is therefore possible that patients presenting with these syndromes will be prioritised for care.

These limitations reflect the real-world challenges of conducting research in developing settings. The proposed study design is an attempt to balance methodological rigour with the practical considerations of emergency care delivery and research at MHPH.

Conclusion

Triage is an essential component of EC systems, especially in developing settings where demand for care typically exceeds the available resources. This study, using pre-post intervention methodology, will determine whether the introduction of a triage system leads to a clinically significant decrease in TTA for selected time-critical syndromes. It will also describe the impact on ED mortality, hospital mortality and total LOS.

A secondary objective of this study is to assess the validity and reliability of the WHO triage scale. There is currently no published data on the performance of this system.

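### The before/after comparison is tested only with unadjusted, independent-visit tests, although the protocol itself names staffing and demand shifts that act on whole days or runs of days

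*Combined protocol and SAP*

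**What the plan says.** The Analysis section (Primary objectives) of the combined protocol and SAP gives the whole comparative analysis. For TTA, a Student's "t-test will be used to compare the difference in TTA for the ten sentinel conditions (assuming parametric data"). For the second form of the primary outcome, "Chi-Square will be used to determine the difference in proportions of patients seen within 15 minutes". ED mortality, hospital mortality and length of stay get one or other of the same two tests. Nowhere is there a covariate, a stratified or standardised analysis, a time-series model, or a clustered or robust variance.

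The Limitations section accepts that the design is open to confounding. It says the new system "may prompt an increase in ED presentations, and a change in the overall acuity of the patient cohort", and its answer is to restrict the primary outcome to ten conditions. It then names "changes in staffing levels and acute fluctuations in demand for emergency care (for instance, in the setting of disaster or outbreak"), and its answer is that, within the researchers' influence, "attempts will be made to control these factors and minimise variation across the study period".

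The Sample size section sets the yardsticks. For TTA: "A clinically significant improvement in the TTA for these patients is thought to be five minutes". For the proportion: "an absolute improvement of 10% (to 55%) will require a sample size of 784 (392 per group"). It plans eight-week periods at about 15 sentinel patients per day.

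**The concern.** There are two separate gaps.

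**Case mix.** Restriction limits drift in overall acuity. It does not hold fixed the mix, severity or arrival hour within the ten conditions, which run from appendicitis to septic shock. If that mix differs between periods, the unadjusted difference can be biased in either direction.

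**Correlation.** Staffing and demand act on whole days, and an outbreak acts on runs of days. Patients arriving on the same or neighbouring days then share part of their waiting time. The planned tests ignore this, so any positive correlation makes their standard errors too small. The unit of analysis is not stated outright, but the tests and the per-group sample sizes only make sense for individual visits.

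At stake is how far a modest observed difference can be trusted. With 840 visits per period, differences far below five minutes can reach significance, so the correctness of p-values and intervals matters most for small effects.

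**Working it through.** **1. The plan's own figures.** Inputs from Sample size: alpha 0.05 (two-sided assumed) and the stated beta of 0.8 read as 80% power. Pooled two-proportion formula:

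n = [1.96·√(2p̄(1−p̄)) + 0.8416·√(p₁(1−p₁)+p₂(1−p₂))]² / (p₁−p₂)²

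- 45% v 55%: (1.3859 + 0.5921)² / 0.01 = 391.3, so 392 per group, as stated.
- 15% v 10%: (0.9167 + 0.3925)² / 0.0025 = 685.6, so 686 per group, as stated.
- 686 × 1.1 / 15 = 50.3 days, matching the stated minimum of 50. Eight weeks give 56 × 15 = 840 per period, 1,680 in all.

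Both figures reproduce under independence. The 10% buffer has no stated purpose and is not described as a design effect.

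**2. An SD for TTA (assumed; none is given).** A lognormal with the plan's mean of 20 minutes and 45% within 15 minutes has sigma 0.643 and SD 14.3 minutes. An SD of 20 is taken as an upper value. The stated 17 per group implies 5·√(17/2)/(1.96+0.84) = 5.2 minutes, but a normal distribution with that SD puts only Φ(−5/5.2) = 17% within 15 minutes, against the plan's 45%. It is not used.

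**3. Case mix (assumed shift).** If the share of a condition that waits 10 minutes longer rises by 5 points, mean TTA moves 0.05 × 10 = 0.5 min with no triage effect. The chance of rejection is P(|Z + 0.5/SE| > 1.96), with SE = SD·√(2/840).

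- SD 14.3: SE 0.70, ratio 0.72, rejection 11%.
- SD 20: SE 0.98, ratio 0.51, rejection 8%.

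**4. Correlation (assumed ICCs, minutes scale).** With independent days, DEFF = 1 + 14·ICC and true alpha = 2·(1 − Φ(1.96/√DEFF)). The last column is simulated: two periods of 56 days, 15 visits a day, a 30-day gap for the pilot month, day-to-day autocorrelation 0.5.

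| ICC | DEFF | Planned test, independent days | Planned test, autocorrelation 0.5 |
|---|---|---|---|
| 0.01 | 1.14 | 6.6% | about 10% |
| 0.02 | 1.28 | 8.3% | about 15% |
| 0.05 | 1.70 | 13.3% | about 27% |
| 0.10 | 2.40 | 20.6% | about 39% |

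If only about 5 visits share the correlation (DEFF = 1 + 4·ICC), the independent-day figures fall to 5.5/5.9/7.4/9.8%.

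With standard errors at week level and t on 14 df, the same simulation rejects in about 5–7%. A fuller simulation with ten conditions, arrival-hour bands, age and sex gives up to about 9%. Clustering on day alone is not enough: with autocorrelation 0.5 the fuller simulation rejects in 9.3/9.9/15.0/19.3%.

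**5. Could correlation alone produce five minutes?** At ICC 0.10, a spurious difference of five minutes or more in either direction occurred in 0 of 20,000 runs with independent days, in 0.16% with autocorrelation 0.5, and in about 2.6% when the SD was also 20.

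**6. Price of week-level errors (unadjusted simulation).**

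| Scenario | 95% half-width, TTA | Power for 5 min |
|---|---|---|
| SD 14.3, no correlation | 1.5 min | at least 97% |
| SD 14.3, ICC 0.10, independent days | 2.3 min | at least 97% |
| SD 14.3, ICC 0.10, autocorrelation 0.5 | 3.1 min | about 87% |
| SD 20, ICC 0.10, autocorrelation 0.5 | 4.3 min | about 61% |

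At SD 14.3 and ICC up to 0.05, power is at least 97% even with autocorrelation 0.5.

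**The case against.** The protocol discloses the confounding, is openly pragmatic, and asks about a clinically significant decrease, which it sets at five minutes. Step 5 shows that correlation alone will rarely produce a difference that large. That stands, and it limits the seriousness of the point.

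Four further objections also stand in part:

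- Extra presentations prompted by triage are a consequence of the intervention, not an outside confounder. Crowding from them would tend to lengthen TTA. The argument therefore rests on the staffing and outbreak sentence and on case mix within the ten conditions.
- A regression on patient characteristics does not adjust for staffing or demand. Clustering only widens the errors on their account.
- The treating clinician assigns the sentinel condition after arrival, partly from oxygen need, blood pressure or procedures (Appendix 3), so triage could affect the label. The Pre-intervention text requires the clinician to mark whether one of the ten applies; it does not clearly say that the form records which one.
- The ICCs, the autocorrelation, the SDs and the 0.5-minute shift are all assumptions.

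A reader might infer that adjustment would isolate the triage effect. It would not: everything else that changes at the single switch date stays confounded with triage. A reader might also infer that the mortality comparison is underpowered. The documents do not support that: 80% power at 686 per group (87% at 840) assumes independent visits, and no ICC for death is available to say how much is lost.

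None of this supplies the missing analysis. Disclosing a limitation does not correct a standard error, and a disaster or outbreak is outside the researchers' control.

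**Conclusion.** The point holds and should be fixed. That no adjusted or correlation-robust analysis is prespecified is certain from the text. The size of the harm is illustrative: it depends on an ICC, an autocorrelation and an SD that the documents do not give, and with no correlation the planned tests keep their 5% level.

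The main risk is a small difference wrongly declared significant, with an interval that is too narrow. Two stronger readings go too far. One is that the planned test is likely to manufacture a five-minute benefit; even the most adverse scenario examined does not show that. The other is that a true five-minute effect can never be missed once errors are computed properly. That is comfortable at SD 14.3 with ICC up to 0.05, but not at SD 20 with strong, persistent day effects.

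**What to change.** Prespecify as the main analysis a regression on period:

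- Linear for TTA, reported in minutes; linear, or logistic with marginal standardisation, for the proportion seen within 15 minutes, reported in percentage points.
- Adjust for age, sex and arrival hour and, if the form records which of the ten applies, sentinel condition. Also report the result without condition.
- Cluster standard errors on consecutive 7-day study weeks counted from the start of each period (8 per period, t on 14 df). Calendar weeks would give nine clusters if a period began mid-week. Add a daily autocorrelation-robust analysis as a check.
- Report adjusted differences with 95% CIs against the five-minute and 10-point targets. Keep the t-test and chi-square as secondary.
- Put initial vital signs, daily attendance and any recorded staffing in sensitivity models only, since triage may alter their timing or level.

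State in the plan that the main model does not adjust for staffing or demand, that no adjustment separates triage from other changes at the switch date, and that the 80% power for mortality assumes independent visits. Confirm that the de-identified export keeps arrival time, condition and a study-day number.

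The cost is wording, a little analysis time and that check. The statistical price is wider intervals, as in the table at step 6. With 16 weeks the method is approximate: rejection rates under no effect were about 5–9% in simulation, not exactly 5%.

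### The sample-size section states beta 0.8 (20% power) three times; the 15-minute and mortality sizes are those for 80% power, and the time-to-assessment size cannot be confirmed without its SD

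*Combined protocol and SAP*

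**What the plan says.** The Sample size section of the combined protocol and SAP gives three calculations, each of them "at an alpha of 0.05 and beta of 0.8".

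- **TTA, the primary outcome.** The mean wait is taken as 20 minutes, and the target is set by "A clinically significant improvement in the TTA for these patients is thought to be five minutes". From this, "a sample size of 34 (17 per group) will be required", for the selected "time-critical conditions at an alpha of 0.05 and beta of 0.8". No SD is given.
- **Proportion seen within 15 minutes.** A rise from 45% to 55% "will require a sample size of 784 (392 per group) at an alpha of 0.05 and beta of 0.8".
- **Mortality.** For a fall of 5 percentage points from 15%, "a sample size of 1372 (686 per group) is required at an alpha of 0.05 and beta of 0.8".

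The section never states power as such, and nothing elsewhere in the document defines beta differently or corrects the term. Sidedness is not stated.

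**The concern.** By convention beta is the probability of missing a true effect of the stated size, and power is 1 − beta. A beta of 0.8 is therefore 20% power, which no one would choose as a design target. Either the label or the sizes must be wrong.

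This is the only place where the plan states its operating characteristics. An ethics committee or a later report that copies the wording would carry a false error rate. A reader who wants the true power has to rebuild the calculations, and for the primary outcome the document does not supply enough to do so.

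**Working it through.** **Inputs, all from the Sample size section.** Alpha 0.05; stated beta 0.8; equal groups; 45% against 55%; 15% against 10%; TTA difference 5 minutes, mean 20 minutes, 17 per group. The Analysis section names chi-square for the 15-minute proportion, chi-square or t-test as appropriate for the secondary outcomes, and Student's t-test for TTA. I assume two-sided tests.

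**Formula for two proportions** (pooled variance, no continuity correction), with p̄ the mean of p1 and p2:

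n per group = [z(0.975)·√(2p̄(1−p̄)) + z(power)·√(p1(1−p1)+p2(1−p2))]² / (p1−p2)²

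with z(0.975) = 1.960, z(0.80) = 0.8416 and z(0.20) = −0.8416.

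**Step 1: reproduce the plan's sizes at 80% power.**

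- 45% against 55%: 1.960 × 0.7071 + 0.8416 × 0.7036 = 1.3859 + 0.5921 = 1.9780. (1.9780/0.10)² = 391.3, so **392**, as stated.
- 15% against 10%: 1.960 × 0.46771 + 0.8416 × 0.46637 = 0.91669 + 0.39251 = 1.30920. (1.30920/0.05)² = 685.6, so **686**, as stated.

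**Step 2: take beta 0.8 literally (20% power).**

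- 45% against 55%: 1.3859 − 0.5921 = 0.7938. (0.7938/0.10)² = 63.0, so **64**.
- 15% against 10%: 0.91669 − 0.39251 = 0.52418. (0.52418/0.05)² = 109.9, so **110**.

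These are about one sixth of the stated sizes (64/392 = 0.16; 110/686 = 0.16).

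**Step 3: could another formula rescue the literal reading?** At 20% power, the one-sided, continuity-corrected and unpooled variants never exceed 82 per group for the 15-minute proportion or 148 for mortality. None comes near 392 or 686.

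**Step 4: TTA, 17 per group.** The size depends on an SD that is not given, so I ran a range, using the two-sided t-test with a 5-minute difference (noncentrality 5/(SD·√(2/17)), 32 degrees of freedom).

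| Assumed SD (min) | Power at 17 per group |
|---|---|
| 5 | 80.7% |
| 6 | 65.4% |
| 10 | 29.3% |
| 12.5 | 20.5% |
| 13 | 19.3% |
| 15 | 15.6% |

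At SD 5, 16 per group gives 78.1%, so 17 is the smallest size that reaches 80%. That makes an SD of 5 with 80% power a likely origin of the figure, but does not prove it. A literal 20% would correspond to an SD between 12.5 and 13.

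**Step 5: does an SD of 5 fit the plan's other figures?** With a normal distribution, mean 20 and SD 5, the share seen within 15 minutes would be Φ((15−20)/5) = Φ(−1) = 15.9%, against the plan's 45%. The distribution is not stated, so I tried two shapes that meet both the mean of 20 and the 45%:

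- *Lognormal with log-scale SD s.* The two conditions give s²/2 + 0.1257s − ln(20/15) = 0, so s = 0.643 and SD = 20·√(exp(0.643²)−1) = 14.3 minutes. Noncentrality is 1.02 and power at 17 per group is about 17%.
- *Normal.* SD = 5/0.1257 = 39.8 minutes, with power about 6%. This is implausible for a wait that cannot be negative, and is shown only as the far end of the range.

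**Step 6: consequences for the study's length.** Mortality sets it: 686 × 1.1 / 15 = 50.3 days, against the stated minimum of 50. That calculation uses the 686 directly, so correcting the label leaves it and the 8-week periods unchanged.

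**The case against.** The best defence is that the intent is plain. The section speaks of sizes needed to demonstrate effects, writing beta for power is a recognisable slip, and any statistician who tests 392 or 686 sees it at once. The slip is one error repeated, not three defects, and the two checkable calculations are arithmetically sound. All of that stands. It bears on how serious the point is, not on whether the text is wrong.

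A reader might infer that the study is planned with an 80% chance of missing each target effect. The documents do not support that. The sizes for the two proportions carry 80% power (80.1% at 392 per group, 80.0% at 686), and the planned periods are built on the larger of them.

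A reader might also infer the opposite: that all three sizes are 80%-power sizes, so one substitution in three places settles the matter. That is not supported either. It is shown for two sizes only. For TTA, 80% rests on an unstated SD of about 5 minutes, which the plan's own baseline figures do not favour.

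**Conclusion.** The point holds as a labelling error. For the 15-minute proportion and mortality, the stated beta contradicts the stated sizes, and beta 0.2 reconciles them exactly, assuming two-sided alpha 0.05 and the pooled formula. The effect on sample size, buffer and study period is nil, so the severity is low.

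For TTA the intended power was probably also 80%, but the document cannot confirm it. At 17 per group the power runs from about 81% (SD 5) to about 17% (SD 14.3, the lognormal that fits the plan's mean and its 45%). The lognormal shape is my assumption.

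This does not mean that the study is too small for TTA. At SD 14.3 the normal approximation gives 2 × (1.960 + 0.8416)² × 14.3² / 5² = 128.4, so about 129 per group for 80% power, well below the 686 per group planned for mortality. What is unsupported is the stated requirement of 34, not the planned enrolment.

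**What to change.** In the Sample size section:

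1. For the 784 and 1372 calculations, replace the beta statement with power of 0.8 (beta 0.2), and add that the tests are two-sided if the sponsor confirms it.
2. For the TTA calculation, make the same replacement only together with the SD that was used, taken from the sponsor's records, and its justification. If that SD cannot be recovered or supported, restate the TTA size or power for an SD that is consistent with the 20-minute mean and the 45% seen within 15 minutes.

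The first change is two wording edits. The second takes a look-up or one short recalculation. Neither alters the 8-week periods, data collection or analysis.
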